[Final v3.0]	 Page 1: Update of CIP version: V4.0 (2021 12 03) Section 5 page 8: Add of "Remote or phone follow-up, medical record review, or follow-up with other healthcare practitioner may be utilized for 1-month, 3-month, 12-month and 24-month visits due to COVID-19 related reasons as explained in the CIP v4.0 and the Addendum VA." Section 7.9 pages 14/15: Removal of "and procedure related adverse events" Add of "Time to Device-related AEs occurrence may also be assessed using Kaplan Meyer estimates." Add of "Hernia recurrence will be assessed during physical examination at 1-month, 3-month, 12-month and 24-month assessment post-surgery. Remote follow-up visits due to COVID-19 related reasons may be performed: if hernia or hernia reoccurrence is suspected during a remote visit using questionnaires, the subject will be instructed to return to the clinic or hospital for diagnosis by the surgeon through clinical assessment. This process is fully accepted by scientific societies^{5,6,7,8,6}". Section 9 pages 17/18: Move of all the references in this section (instead of footnotes) and add of new references related to remote visits. 	[name], Sr Biostatistician, Global Clinical Data Solutions

Version [Final v3.0]

2. List of Abbreviations and Definitions of Terms

Term/Abbreviation	previation Definition					
ADE	Adverse device effect - Adverse event related to the use of an investigational medical device. NOTE 1: This definition includes adverse events resulting from insufficient or inadequate instructions for use, deployment, implantation, installation, or operation, or any malfunction of the investigational medical device. NOTE 2: This definition includes any event resulting from use error or from intentional misuse of the investigational medical device					
AE	Adverse event - Any untoward medical occurrence, unintended disease or injury, or untoward clinical signs (including abnormal laboratory findings) in subjects, users or other persons, whether or not related to the investigational medical device. NOTE 1: This definition includes events related to the investigational medical device or the comparator. NOTE 2: This definition includes events related to the procedures involved. NOTE 3: For users or other persons, this definition is restricted to events related to investigational medical devices.					
ASA	American Society of Anesthesiologists					
CCS	Carolina Comfort Scale: it is a validated, disease-specific, quality of life (QOL) questionnaire developed for patients undergoing hernia repair.					
CE Mark	European Community Marking that indicates that the product (device) complies with the European Legislation and so can go to EU market.					
CI	Confidence Interval					
CIP	Clinical Investigation Plan (can be used synonymously with Protocol)					
Device Deficiency	Inadequacy of a medical device with respect to its identity, quality, durability, reliability, safety or performance. Note: Device deficiencies include malfunctions, use errors, and inadequate labeling.					
FAS	Full Analysis Set – An analysis set including any subjects enrolled and receiving study device					
Hernia recurrence	A clinically manifested bulge or a protrusion exacerbated by a Valsalva maneuver.					
IA	Interim Analysis					
IRB	Institutional Review Board					
ISO	International Organization for Standardization					

Version [Final v3.0]

Page 5 of 18

Term/Abbreviation	Definition
PMCF	Post market clinical follow up
PPAS	Per Protocol Analysis Set – An analysis set consisting of a subset of the full analysis set of subjects who meet the primary endpoint (12-month assessment) and who did not deviate (major) from the protocol
QOL	Quality of Life
SAE	 Serious Adverse Event - Adverse event that: a. Led to a death, b. Led to a serious deterioration in the health of the subject, that either resulted in: Resulted in a life-threatening illness or injury, or Resulted in a permanent impairment of a body structure or a body function, or In-patient or prolonged hospitalization, or Medical or surgical intervention to prevent life threatening illness or injury or permanent impairment to a body structure or a body function, or Led to fetal distress, fetal death or a congenital abnormality or birth defect. Note: Planned hospitalization for a pre-existing condition, or a procedure required by the CIP, without serious deterioration in health, is not considered a serious adverse event.
SADE	Serious Adverse Device Effect - Adverse device effect that has resulted in any of the consequences characteristic of a serious adverse event.
SAP	Statistical Analysis Plan
SAS	Safety Analysis Set is an analysis set including any subject pre-operatively eligible for the study and with skin incision, including those who are 'screen failure during surgery.
USA	United States of America
UADE	Unanticipated Adverse Device Effect - Any serious adverse effect on health or safety or any life threatening problem or death caused by, or associated with, a device, if that effect, problem, or death was not previously identified in nature, severity, or degree of incidence in the CIP or application (including a supplementary plan or application), or any other unanticipated serious problem associated with a device that relates to the rights, safety or welfare of subjects.
USADE	Unanticipated Serious Adverse Device Effect - Any serious adverse device effect which by its nature, incidence, severity or outcome has not been identified in the current version of the risk analysis report. Note: Anticipated serious adverse device effect (ASADE) is an effect which by nature, incidence, severity or outcome has been identified in the risk analysis report.

PPDS Statistical Analysis Plan	
Version [Final v3.0] Page 6 of 18	Medtronic

Term/Abbreviation	Definition
Ventral Hernia	A ventral hernia is a hernia of the abdominal wall excluding the inguinal area, the pelvic area and the diaphragm.

3. Introduction

A ventral hernia is a hernia of the abdominal wall excluding the inguinal area, pelvic area, and the diaphragm. It is comprised of an abnormal protrusion of abdominal cavity contents or pre-peritoneal fat through a defect or weakness in the abdominal wall. Hernias may occur spontaneously (primary hernia) or at the site of a previous surgical incision (incisional hernia).

Hernias can only be repaired by surgical procedure. Operative repair of abdominal wall hernias forms a part of the daily routine practiced by every general and visceral surgeon. Approximately 4 million laparotomies are performed in the United States annually, up to 30%- 45% of them resulting in incisional hernia. Approximately 250,000 ventral incisional hernia repairs are performed annually in the United States. The repair of ventral hernias can be performed through either an open or a laparoscopic technique by a simple interrupted suture repair or a mesh repair.

Use of prosthetic mesh repair is considered as standard of care for ventral hernia treatment.

Depending on the surgical technique, the mesh may be implanted either in an intraperitoneal position, or outside of the abdominal cavity, such as onlay or inlay techniques. Surgical meshes are medical devices used to provide additional support to weakened or damaged tissue. The majority of surgical mesh devices currently available for use are constructed from synthetic materials and/or animal tissue. The mode of action of the mesh primarily relies on the strength provided by the structural component of the implant, i.e. the textile/tissue structure. The surgical mesh is intended to be progressively colonized by the host tissue following the cascade of biological mechanisms inherent to the wound healing and soft tissue remodeling, so that the mesh will ensure a long-term reinforcement of soft tissues.

Currently, various surgical mesh designs exist to accommodate the variety of surgical techniques in soft tissue repair and reconstruction by open and laparoscopic surgeries. In particular, composite meshes such as Parietene[™] DS Composite Mesh, are composed of a textile with a temporary adhesion barrier on one side to allow intraperitoneal mesh placement during abdominal wall surgery while minimizing tissue attachment to the mesh in case of direct contact with the viscera.

PPDS Statistical Analysis Plan		
Version [Final v3.0]	Page 7 of 18	Medtronic

The development of Parietene[™] DS Composite Mesh relies on the long-term knowledge acquired by Medtronic in the development of surgical mesh for a variety of soft tissue repair procedures and the processing of implantable absorbable polymers. Parietene[™] DS Composite Mesh was specifically developed as a fully synthetic alternative to the composite meshes currently available.

Medtronic has conducted a biocompatibility evaluation of Parietene[™] DS Composite Mesh, compliant with the standard EN ISO 10993-1 (2009), which demonstrates the biological safety of the device. Pre-clinical animal testing comparing of Parietene[™] DS Composite Mesh and Proceed[™] Surgical Mesh (Studies 197164, 197165 and 198929), its predicate device, demonstrate that Parietene[™] DS Composite Mesh achieves at least equivalent performance in terms of tissue integration and minimizing tissue attachment in case of contact to the viscera.

Parietene[™] DS Composite Mesh obtained 510 K clearance in US (June 2017).

The post-market study on Parietene[™] DS Composite Mesh in the US will serve to confirm the Safety and Performance of the product in the short, mid and long term for the repair of primary and incisional ventral hernia and to support EU regulatory approval and post-market requirements through a prospective single-arm study on N=125 male or female adult subjects will be enrolled at a minimum of 4 USA sites who are undergoing elective ventral hernia repair.

This document outlines the detailed statistical methods to be implemented for the data collected within

the scope of the PPDS study. The Clinical Investigation Plan (CIP) document was used to create the Statistical Analysis Plan (SAP).

4. Study Objectives

4.1. Primary Objective

The primary objective of this study is to assess hernia recurrence, within 12 months following the use of Parietene[™] DS Composite Mesh in ventral hernia repair.

4.2. Secondary Objective

The secondary objective of this study is to assess clinical outcomes, within 24 months following the use of Parietene[™] DS Composite Mesh in ventral hernia repair.

Version [Final v3.0]

5. Investigation Plan

This study is a single arm, prospective, multi-center, observational, US post-market study to confirm the clinical safety and performance of Parietene[™] DS Composite Mesh in ventral hernia repair.

After IRB approvals, subjects who have signed an informed consent form (and who meet the eligibility criteria) and have received Parietene[™] DS composite mesh will be enrolled in the study. Subjects will undergo elective ventral hernia repair using Parietene[™] DS Composite Mesh and be evaluated pre-operatively, at the procedure, at discharge, within 1 month, 3 months, 12 months and 24 months post-surgery. Remote or phone follow-up, medical record review, or follow-up with other healthcare practitioner may be utilized for 1-month, 3-month, 12-month and 24-month visits due to COVID-19 related reasons as explained in the CIP v4.0 and the Addendum VA.

An interim analysis based on 30 subjects with complete 3-month visits to assess the short-term safety of the device will be used to support EU regulatory approval. Study enrollment will continue during interim analysis. The study will continue as a post market clinical follow up (PMCF) with extended follow-up of subjects to assess the mid (12 months) and long (24 months) term safety and performance of the device. The study will include a minimum of 125 subjects who will be followed 24 months post-surgery at a minimum of 4 USA sites. Subject participation in the study will last a maximum of 26 months and overall, the study is estimated to proceed for up to 38 months.

Procedure/Assessment	Screening (Day-30 to 0)	Operative (Day 0)	Discharge Assessment	1 Month (±14 days) Follow-up	3 Month (±14 days) Follow-up	12 months (±30 days) Follow-up	24 months (±30 days) Follow-up
	Can be combined			(Visit)	(Visit)	(Visit)	(Visit)
Eligibility criteria	X1	X1					
Informed consent	X ²						
Subject demographics	Х						
Pregnancy status	X1	X1					
Medical and abdominal surgical history and relevant risk factors	x						
Carolina Comfort Scale™ (Appendix B)	x			х		х	Х
Hernia defect description		Х					
Recurrence history if applicable		Х					
Date of surgery, Operative time		Х					
Anesthesia / ASA grade		Х					
Intraoperative wound contamination class		х					
Indication for ventral hernia surgery		х					

Study procedures and assessment are described in the study schematic below:

Page 8 of 18

		Version	[Final v3.0]		Page 9 o	f18		Medtronic
Procedure/Assessment (D	Screening Pay-30 to 0)	Operative (Day 0)	Discharge Assessment	1 Month (±14 days) Follow-up	3 Month (±14 days) Follow-up	12 m (±30 Follo	onths days) w-up	24 months (±30 days) Follow-up
	Can be con	nbined		(Visit)	(Visit)	(Vi	sit)	(Visit)
Type of access, defect closure and Surgical technique approach		х						
Mesh size, lot number, positioning and fixation		х						
Antibiotic prophylaxis		Х						
Area of mesh overlap		Х						
Surgeon satisfaction questionnaire		х						
Adverse events assessment		Х	Х	Х	Х	>	K	Х
Length of hospital stay			Х					
Hernia recurrence/reoperation				Х	Х	>	κ	Х
Study exit								X

6. Determination of Sample Size

Sample size has been determined based on an acceptable level of accuracy for the estimated rate of hernia recurrence at 12 months (primary endpoint).

Previous studies^{1,2} of the predicate device (Proceed[™] Surgical mesh) with similar study indications, population, and design (prospective study with a long-term follow-up with more than 100 subjects), have reported the incidence of recurrence at 12 months to range from 3.5% to 5.2%.

95% confidence intervals obtained from incidence rates between 3.5% and 5.2% with N=100 subjects are shown below. Precision of the recurrence rates range from \pm 3.6% to \pm 4.4% as the recurrence rate increases.

	Recurrence rate at 12-month (1 year)								
	3.5% 4.0% 4.5% 5.2%								
N	100	100	100	100					
95% CI	[0.0 % - 7.1 %]	[0.2% - 6.7%]	[0.4% - 8.6%]	[0.8% - 9.6%]					
accuracy (+/-)	3.6%	3.8%	4.1%	4.4%					

Anticipating an attrition rate of 20% at 12 months, 125 subjects will be enrolled for this study.

PPDS Statistical Analysis Plan	
Version [Final v3.0] Page 10 of 18	Medtronic

7. Statistical Methods

7.1. Study Subjects

7.1.1. Disposition of Subjects

Summaries of screened, consented and enrolled subjects will be provided overall.

Subjects in the Safety Analysis Set (SAS), in the Full Analysis Set (FAS), and in Per protocol Analysis Set (PPAS) will be summarized, according to follow-up, and within each investigational site.

Reason for study discontinuation will be tabulated based on FAS and SAS.

7.1.2. Clinical Investigation Plan (CIP) Deviations

Subjects with protocol deviations will be summarized and protocol deviations will be reported by type on overall FAS subjects and distinguishing minor and major protocol deviations/violations.

Major protocol deviations and violations will be defined and identified by the study team prior to run statistical analysis, based on protocol deviations listing provided by statistician.

Version [Final v3.0]

7.1.3. Analysis Sets

Statistical analysis will be performed on:

- Full Analysis Set (FAS): including any subject enrolled and receiving study device, representing the primary analysis population, for Efficacy and Safety analyses
- Per Protocol Analysis Set (PPAS): a subset of the FAS of subjects who meet the primary endpoint (12month assessment) and who did not deviate (major) from the protocol, as confirmatory analysis for Efficacy and Safety analyses,
- Safety Analysis Set (SAS): any subject pre-operatively eligible with skin incision including those who are 'screen failure during surgery', used for Safety analysis.

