10.10 Recording Data

This study will utilize an electronic database and eCRFs. All data requested on the eCRFs are required. Study visits or measurements not collected and/or recorded will be considered deviations unless otherwise specified. The Principal Investigator or authorized designee(s) must ensure the accuracy and completeness of the recorded data and then provide his/her electronic signature on the eCRFs. Changes to data previously submitted to the sponsor will require a new electronic signature by the Investigator to acknowledge/approve the changes.

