14.3.2 Secondary Endpoints

- Incidence of ADEs intra-operatively will be calculated on the FAS subjects who reach the corresponding time point, including any subject experiencing hernia recurrence, AEs or ADE within the corresponding follow-upperiod.
- Incidence of hernia recurrences will be calculated on the FAS subjects who reach the corresponding time point.
- Time to hernia recurrence, as well as time to AE occurrence analyses will be run using Kaplan Meier estimate and curve.
- Subject quality of life (QoL) questionnaires will be evaluated using the Carolinas Comfort
 Scale™ (Appendix B), and statistical analysis will follow the corresponding analysis guideline.
- Length of hospital stay will be summarized using count, mean, standard deviation, median, minimum, and maximum.

Subgroup analyses on secondary endpoints will be performed according to study needs and will be described in the statistical analysis plan and the clinical study report.

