14.4 Safety Assessment

Most of the safety endpoints are part of secondary endpoints and method of evaluation are described above.

Incidence of Adverse device effect, as well as SAEs, and SADEs will be calculated on the Full Analysis Set, Safety Analysis Set and Per protocol Analysis Set and summarized by counts and percentages.

MDT17051PDS Version 4.0 Page 43 of 56

Listings of AEs will be generated including event description, severity and seriousness, relation to procedure, relation to the device and outcome.

In the case that a subject becomes pregnant postoperatively, a deviation will be submitted, and they will be followed for safety assessment. They will not be included in the primary or secondary endpoint analyses.

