7.9. Evaluation of Objectives

Study objectives will be assessed through study endpoints measurement.

The primary endpoint is incidence of hernia recurrence within 12 months following Parietene[™] DS Composite Mesh use in ventral hernia repair.

Incidence of hernia recurrence within 12 months will be measured on the FAS subjects and using the following calculation formula:

[Subjects with Recurrence diagnosed within the first 12month following surgery]

[Subjects with Recurrence diagnosed within the first 12month following surgery + Subjects free of recurrence with a follow-up ≥12months]

A confirmatory analysis of primary endpoint will be run using Per Protocol Analysis Set.

Secondary endpoints

- Incidence of adverse device effects (ADEs) intra-operatively, at discharge, within 1 month, 3 months, 12 months, and 24 months following Parietene[™] DS Composite mesh use in ventral hernia repair will be primarily assessed based on FAS, and secondarily using PPAS and SAS.
- Incidence of hernia recurrence at 1, 3 and 24 months. The evaluation of hernia recurrence will be performed during a physical examination, using the formula described previously, according to the different time-points, and based on FAS and PPAS.
- Time to hernia recurrence and time to adverse device effect occurrence (from surgery time-point), will be assessed using Kaplan Meyer estimates. FAS and PPAS will be used for time to hernia recurrence, while FAS, PPAS and SAS will be used for time to ADE occurrence analysis. Time to Device-related AEs occurrence may also be assessed using Kaplan Meyer estimates.
- Carolinas Comfort Scale[™] QOL questionnaires completed pre-operatively and at 1, 12 and 24 months postoperatively will be analyzed using the Carolina Comfort Scale User Guide recommendations and programming code (see Appendix B), and based on FAS and on PPAS.

Several Subgroup analyses will be performed. Comparative analyses will be performed by hernia type (primary hernia versus incisional hernia) on overall subjects and on a subgroup of subjects with robotically assisted laparoscopic repair. Results of subjects operated with robotically assisted laparoscopic repair will also be compared with subjects operated with a traditional Laparoscopic procedure.

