Hernia recurrence will be assessed during physical examination at 1-month, 3-month, 12-month and 24-month assessment post-surgery. Remote follow-up visits due to COVID-19 related reasons may be performed: if hernia or hernia reoccurrence is suspected during a remote visit using questionnaires, the subject will be instructed to return to the clinic or hospital for diagnosis by the surgeon through clinical assessment. This process is fully accepted by scientific societies^{5,6,7,8,9}

7.10.Safety Evaluation

Safety will be assessed as the proportion of subjects with AE based on the FAS, PPAS and SAS; AE incidence will be reported overall, and according to:

- Relation to the procedure
- Relation to the device including anticipated and unanticipated ADEs,
- Severity,
- Seriousness.

PPDS Statistical Analysis Plan	
Version [Final v3.0] Page 16 of 18	Mectronic

Listing of AEs, SAEs, ADEs and SADEs, and UADEs will be provided based on FAS, PPAS and SAS, using the MEDRA coding system classification for AE terms, and including characteristics described previously and AE outcome.

7.11.Health Outcomes Analyses

Health outcomes analyses are already part of primary and secondary endpoints analyses, as described previously.

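### The per-protocol set requires the 12-month assessment but is also used for early safety, 1- and 3-month recurrence and time-to-event outputs, where it selects on later follow-up

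*SAP*

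**What the plan says.** SAP 7.1.3 defines the PPAS as "a subset of the FAS of subjects who meet the primary endpoint (12month assessment) and who did not deviate (major) from the protocol" and calls it confirmatory for both efficacy and safety. Protocol 14.1 and the glossaries of both documents carry the same condition. The protocol synopsis omits the reference to the 12-month assessment.

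The set is then applied to outputs that start at surgery:

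- ADE incidence, intra-operative to 24 months (SAP 7.9): "will be primarily assessed based on FAS, and secondarily using PPAS and SAS".
- Recurrence at 1, 3 and 24 months (SAP 7.9): "according to the different time-points, and based on FAS and PPAS".
- Kaplan-Meier analyses (SAP 7.9): time to recurrence on FAS and PPAS, while "FAS, PPAS and SAS will be used for time to ADE occurrence analysis".
- AE proportions (SAP 7.10): "Safety will be assessed as the proportion of subjects with AE based on the FAS, PPAS and SAS".
- Incidence of ADEs, SAEs and SADEs (protocol 14.4): "will be calculated on the Full Analysis Set, Safety Analysis Set and Per protocol Analysis Set".

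Neither document gives a different per-protocol definition for safety, early time points or time-to-event outputs.

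Three other provisions matter. Protocol 14.3.2 gives an ADE denominator: incidence "will be calculated on the FAS subjects who reach the corresponding time point, including any subject experiencing hernia recurrence, AEs or ADE" in the period. Its sentence names only intra-operative ADEs, so applying it at later time points is an interpretation. Protocol 10.10 says "Study visits or measurements not collected and/or recorded will be considered deviations unless otherwise specified". SAP 7.1.2 leaves it to the study team to decide, before the analysis is run, which deviations are major.

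**The concern.** Whether an intra-operative ADE counts on the PPAS depends on follow-up up to a year later. That is selection on later follow-up, not on adherence to the protocol. A subject with an early ADE who withdraws at month 4 without a recurrence is removed together with the ADE. In the Kaplan-Meier analyses, such a subject should contribute time at risk until exit and then be censored. Here the subject contributes nothing.

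A confirmatory set is useful if a difference from the FAS can be attributed to major deviations. For these outputs the difference would also reflect who stayed to month 12 and which events went with those who left.

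The wording is also open to two readings. Meeting the primary endpoint may mean attending the 12-month assessment. It may instead mean being evaluable under the SAP 7.9 formula, that is, having a recurrence within 12 months or being recurrence-free with at least 12 months of follow-up. An early leaver without a recurrence is outside the set either way. An early leaver with a recurrence is out under the first reading and in under the second.

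**Working it through.** **Inputs from the documents.** 125 enrolled and 20% attrition at 12 months (SAP 6, protocol 14.5); 100 evaluable (same sections); expected 12-month recurrence 3.5% to 5.2% (same sections). The documents give no ADE rate, exit timing, or relation between exit and events. Those are assumptions below.

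**1. The plan's own figure.** 100 / (1 − 0.20) = 125, as stated. The planned number of early leavers is 125 − 100 = 25. This is an upper figure for the subjects affected, because protocol 10.6 allows remote contact or record review to serve for the 12-month visit, and because a leaver with a recurrence may stay in the set.

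**2. Kaplan-Meier recurrence, evaluable reading.** Assume constant hazards and dropout independent of recurrence. Let r be the true 12-month recurrence.

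- Hazards over 12 months: h = −ln(1 − r) for recurrence and c = −ln(0.80) = 0.2231 for dropout.
- Recurrence observed before exit: O = h/(h + c) × [1 − (1 − r) × 0.80].
- Still followed and recurrence-free: S = (1 − r) × 0.80.
- The PPAS has no censoring before month 12, so its Kaplan-Meier estimate at month 12 is O/(O + S).

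r = 3.5%: h = 0.0356, S = 0.7720, O = 0.0314. PPAS = 0.0314/0.8034 = 3.9%.

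r = 5.2%: h = 0.0534, S = 0.7584, O = 0.0467. PPAS = 0.0467/0.8051 = 5.8%.

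Recurrences are kept and recurrence-free leavers are dropped, so the estimate rises although dropout is uninformative. With all subjects included and censored at exit, the target is r itself. Under the attendance reading, independent dropout removes both kinds of leaver in proportion and there is no bias.

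**3. Recurrence at month 3 (illustration).** Assume 2 recurrences by month 3, and 25 subjects leaving between months 3 and 12, one of them with a recurrence. FAS: 2/125 = 1.6%. PPAS: 1/100 = 1.0% if the visit is required, 2/101 = 2.0% if evaluable. Without the 12-month condition: 2/125 = 1.6%.

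**4. ADE incidence (illustration).** Assume a true rate of 15% (18.75 of 125), all ADEs occurring before exit, 20% attrition, no major deviations and no early leavers retained for a recurrence. Subjects with an ADE leave k times as often as others. Then p0 = 0.20/(0.85 + 0.15k) and p1 = k × p0.

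- PPAS as written: 0.15 × (1 − p1)/0.80.
- Protocol 14.3.2 denominator, counting among leavers only those with an ADE: 18.75/(100 + 18.75 × p1).
- All subjects in the set: 18.75/125 = 15.0%.

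| k | PPAS as written | 14.3.2 denominator | All subjects |
|---|---|---|---|
| 0.5 | 16.7% | 18.4% | 15.0% |
| 1 | 15.0% | 18.1% | 15.0% |
| 1.5 | 13.5% | 17.8% | 15.0% |
| 2 | 12.2% | 17.6% | 15.0% |
| 3 | 10.1% | 17.3% | 15.0% |

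The PPAS error has no fixed sign and is zero at k = 1. The 14.3.2 denominator overstates at every k, including k = 1, because it keeps leavers with an event and drops those without. Leavers with other AEs or a recurrence also enter that denominator and lower its figure, which reaches 15.0% only if all 25 leavers count.

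For scale, the 95% half-width at 15% and N = 100 is 1.96 × √(0.15 × 0.85/100) = 7.0 points.

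**The case against.** The strongest reply is that nothing rests on these outputs. The SAP describes the endpoint analysis as descriptive, the FAS is primary, the PPAS is secondary or confirmatory, and ADE and AE results are also produced on the Safety Analysis Set. Neither of the other sets has a 12-month condition. This stands, and it is why the weight is low. It does not make the PPAS outputs interpretable.

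A second reply is that a 12-month condition suits a set built for a 12-month endpoint. That also stands, for the confirmatory analysis of the primary endpoint. It does not extend to intra-operative ADEs or to a survival curve.

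Three stronger readings are tempting and are not supported:

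- A reader might infer that the plan contradicts itself, because protocol 10.12.3 says data up to exit will be analysed and 14.3.2 retains subjects with events. The first does not promise use in every analysis set, and the second is a FAS rule. Neither is breached.
- A reader might infer that early harms disappear from the report, or that the PPAS understates them. The FAS and the Safety Analysis Set keep those subjects, and the direction of any ADE or AE bias cannot be derived from the documents.
- A reader might infer that the cure is to carry the 14.3.2 denominator over to the PPAS. The table above shows that this can be worse than the current wording.

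The documents also do not say that a missed 12-month visit is a major deviation. They leave it open, which is reason enough to settle it.

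**Conclusion.** The point holds as a low-weight clarification. As written, the PPAS safety, 1- and 3-month recurrence and time-to-event outputs select on follow-up to month 12. They exclude up to about 25 of 125 subjects and lose almost all censoring before month 12.

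Under the evaluable reading there is a definite upward bias in the PPAS Kaplan-Meier recurrence estimate, of about 0.4 points at 3.5% and 0.6 points at 5.2%, assuming constant hazards and independent 20% dropout. Under the attendance reading, bias needs a link between leaving and events, and can go either way. The ADE figures illustrate the mechanism and do not predict its size. Only supportive outputs are affected, and the FAS result for the primary endpoint is untouched.

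**What to change.** 1. Keep the 12-month condition only for the confirmatory analysis of the 12-month primary endpoint, and say whether it means attending the assessment or being evaluable under the SAP 7.9 formula.
2. For PPAS safety, 1- and 3-month recurrence and time-to-event outputs, use FAS subjects without a major protocol deviation, with no 12-month condition. State that early exit or a missed 12-month visit is not by itself a major deviation for these outputs. Otherwise protocol 10.10 and SAP 7.1.2 together could exclude the same subjects again.
3. In the Kaplan-Meier analyses, include all these subjects and censor at exit.
4. For ADE and AE incidence on this set, report the Kaplan-Meier cumulative incidence at each time point, or the proportion among all subjects in the set. Do not carry over the protocol 14.3.2 denominator. The simple proportion counts nothing after exit, so the Kaplan-Meier figure is the safer choice at later time points. SAP 7.9 already plans Kaplan-Meier time to ADE on the FAS, so a like-for-like comparison is available.
5. Record the change in SAP 7.12 and align protocol 14.1, the synopsis and both glossaries.

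The cost is wording in two documents, with no new data or subjects. PPAS figures may shift slightly, and the PPAS denominator will differ between the primary endpoint and the other outputs, which table footnotes should state.
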